6.2 Notification by Sponsor of Subject Screening Pass or Fail

Prior to subject being scheduled for the procedure, the Sponsor will review submitted screening and baseline medical information, TTE, TEE, and CT images to confirm anatomic and procedural suitability of the subject for the Tendyne device. Sponsor will notify Investigator when subject passes or fails the screening review.

7 TREATMENT AND PRE-DISCHARGE VISITS

Subjects that pass the screening review will undergo a procedure to implant the Tendyne device.

7.1 Concomitant Procedures

Pre-procedural planning and assessment of MAC may determine that concomitant mitral annulus valvuloplasty is required to ensure mobility of calcification prior to Tendyne valve implantation. In such cases, standard institutional techniques may be used.

7.2 Tendyne Procedure

The valve should be implanted with sterile techniques using primarily TEE guidance. In addition, TTE and fluoroscopic imaging modalities may be used.

Implantation of the valve will be performed by the local site heart team, with an experienced cardiac surgeon trained to perform transapical procedures and jointly with an experienced interventional cardiologist and echocardiographer. Sponsor personnel will be available for procedural support for all Tendyne cases. For a comprehensive description of the Tendyne procedure, refer to the Tendyne Mitral Valve System IFU.

Note: Prior to performing the procedure, all investigators must undergo training by the Sponsor on the Tendyne System and on the CIP. In addition, all investigators must read and understand the IFU that accompanies the device.

Subjects will be prepared for the procedure as per the institution's standard practice for a transapical therapeutic intervention and TEE.

The subject must be on anticoagulant/antiplatelet therapy appropriate for transapical therapeutic interventions. Activated clotting time (ACT) is to be maintained at >300 seconds for the duration of the procedure.

7.2.1 Tendyne Procedure - Access

An 8 Fr. sheath is placed in the apex at the orthogonal access location determined by CT. A 7 Fr. Fogarty catheter is then inserted, leading with the balloon until the mitral annulus is crossed. A 0.035 standard J wire is then advanced into either a pulmonary vein or coiled in the atrium.

Once the J wire is in place, the Fogarty catheter is used to determine a chord-free path has been achieved by retracting/advancing over the wire. Once an entanglement free pathway has been achieved, the Fogarty balloon is deflated and removed. The 8 Fr. sheath is also removed and the Tendyne sheath is inserted.

7.2.2 Tendyne Procedure - Device Delivery

The delivery system is inserted into the Tendyne sheath and aligned for pre-planned rotation of the valve. Both the sheath side port and the delivery system are de-aired and the flush is open until the valve is advanced to the tip of the delivery sheath.

Clocking is performed in the 3D enface view. The valve is then incrementally advanced until the A2 portion of the Tendyne valve is clocked to the center of the "D" shape of the mitral annulus. Using an X-plane echo image, the Tendyne valve is seated intra-annularly and the deployment of the valve is completed.

When the valve is fully deployed, a full echo assessment is made to evaluate PVL, LVOT obstruction and MR resolution. At this point, the valve can be recaptured and can be adjusted if needed. When valve position has been optimized, the delivery system is removed.

7.2.3 Tendyne Procedure - Tensioning

Tension is adjusted using the apical pad tool to attain proper seating of the valve for mechanical stability and optimal paravalvular sealing. Once stability is achieved and valve function is determined to be acceptable, the instrument is removed and the apical pad is fastened to the tether.

Note: The valve can be retrieved at any point during delivery and tensioning up to the point when the tether is cut just prior to surgical site closure.

7.2.4 Tendyne Implant Identification Card

At discharge, each subject implanted with a Tendyne device must be provided with an Implant Identification Card. An Implant Identification Card is included in the package with each Tendyne Mitral Valve System. The subject should be instructed to keep this Implant Identification Card on their person at all times. The serial number of the implanted Tendyne device should be recorded on the Implant Identification Card.

7.3 Procedural Data Requirements

The following procedural information should be recorded on the appropriate eCRF(s) after implant or attempted implant of the Tendyne device.

7.3.1 12-Lead ECG

A 12-lead ECG will be performed pre- and post-valve implant. If prolonged hospitalization occurs after the procedure, the ECG may be collected within 10 days after the index procedure.

7.3.2 Intraoperative Hemodynamic Measurement

During the procedure to implant the Tendyne device, subjects will undergo right-heart catheterization to measure hemodynamics intraoperatively. Cardiac output (CO), pulmonary arterial (PA), aortic and right arterial (RA) pressures will be measured before and after the valve placement via the right heart catheter. LV pressures should be measured via a pigtail catheter.

7.3.3 Intraoperative Angiography

Per investigator discretion, subjects may undergo left-heart catheterization with radiographic imaging before and after the Tendyne valve placement to assess the LV and mitral valve competence. Care must be taken to minimize the amount of contrast media injected into subjects with compromised renal function. Therefore, left ventriculogram procedures described in this protocol are optional.

Tendyne will provide specific instruction on intraoperative imaging requirements as part of investigator training.

7.3.4 Additional Procedural Data Collection

In addition to the intraoperative imaging and hemodynamic measurements, the following procedural information should be recorded:

- General procedure information
- Treatment and Control group implant information
- Laboratory and clinical tests
- Antiplatelet/Anticoagulation medications
- Concomitant cardiovascular medications
- Fluoroscopy duration
- Adverse events, if applicable

- Protocol deviations, if applicable
- Device deficiency, if applicable

7.3.5 Immediate Post-Operative Care

Blood pressure is to be closely monitored and maintained below 135 mmHg systolic during the immediate post-operative period, if possible. The subject's ACT should also be monitored in accordance with hospital protocols.

Subjects will receive standard post-cardiac transapical care as judged appropriate by the investigator.

7.3.6 Anticoagulation Regimen

Subjects receiving the Tendyne device are required to be on anticoagulation therapy, warfarin, with a target INR range of 2.5 to 3.5, for a minimum of six months. A single antiplatelet therapy (aspirin or alternate agent) should also be administered immediately after the procedure and may be continued indefinitely.

Notes:

- During the period of required anticoagulation as stated above, a subject's anticoagulation regimen may be altered or stopped only if medically indicated, however, it should be restarted as soon as possible per physician's discretion.
- For subjects who receive the Tendyne device, a TTE must be performed between 60 and 120 days after anticoagulation stoppage.
 - If the TTE indicates increased gradients (e.g. mitral valve gradient > 6mmHg) or leaflet mobility concerns are identified, a gated CT (4D with contrast) must be performed to evaluate leaflet thrombosis resulting in hypoattenuated leaflet thickening or motion.
 - For subjects with renal insufficiency, a TEE must be performed

7.3.7 Pre-Discharge

Pre-discharge data collection is to be performed within 72 hours prior to discharge from implanting hospital. Pre-discharge data requirements include:

- A physical exam including an assessment of subject's cardiac status and sitting vital signs
- Concomitant cardiovascular medications
- 12-lead ECG
- Laboratory and clinical tests
- Adverse events, if applicable
- Protocol deviations, if applicable
- Device deficiency, if applicable

8 FOLLOW-UP FOR EVALUATION OF SAFETY AND EFFECTIVENESS

8.1 Clinical Follow-up

Follow-up visits are required at 30 days, 3 months, 6 months, 1 year, and then annually through 5 years (**Table 2**); visits will be calculated from the date of the index procedure. Follow-up assessments can be performed at any point in the window, and should be conducted, whenever possible, by the same individual who performed the baseline tests. For a complete schedule of study assessments occurring at each visit, refer to **Appendix III: STUDY Assessment and Follow-up Schedule**.

Subjects should be followed at the investigational site where the subject was registered, and may be followed at another investigational site only with prior agreement from both the new site's Principal Investigator and approval from the Sponsor.

All registered subjects should continue to be monitored and treated per applicable standards of care consistent with the subject's condition. Subjects should be followed by the site investigators at all scheduled follow-up visits and be evaluated for device function.

Note: If a subject has an unsuccessful Tendyne device implant, they should remain in the study and continue to be followed per the study follow-up schedule.

8.2 30 Day, 3 Month, 6 Month, and Annual Visits

Subjects should continue to take baseline medications as clinically (medically) necessary. Required tests and procedures outlined below must be completed. All visits and tests must be completed within the visit window specified in **Table 2**, even if the subject is in hospital.

- A physical exam including an assessment of subject's cardiac status and sitting vital signs
- Concomitant cardiovascular medications assessment
- NYHA Functional Classification assessment
- Blood tests performed, including: BNP or NT-proBNP, plasma free hemoglobin, serum creatinine, INR, CK-MB and Troponin (Type I or T)
- TTE
- 12-lead ECG
- Cardiac CT (**Note:** Required at 30 day visit – an additional CT may be required if anticoagulation regime is stopped, refer to **Section 7.3.5 - Immediate Post-Operative Care**)
- KCCQ questionnaire
- 6-Minute Walk Test
- Modified Rankin Scale (Assessment to be completed after onset of stroke)
- Assess and record adverse events
- Assess and record protocol deviations

Echocardiography images (TTE) obtained at each follow-up visit should be submitted in a timely manner. Throughout the course of the study, the Echocardiography Core Lab may provide feedback to sites regarding quality of images obtained.

During the follow-up period, if a subject requires a cardiac procedure (e.g. MV surgery, permanent LVAD, heart transplant) which may or may not result in explant of the Tendyne device, the subject will remain in the study and continue to be followed.

Every attempt must be made to ensure study subjects do not miss a scheduled follow-up visit. If a subject is unable to complete a visit, the site may attempt to contact them remotely to document their status (e.g., alive) and to administer study questionnaire (KCCQ). This should only be performed in rare instances and the Sponsor should be notified of such instances in advance.

Subjects who do not complete a required follow-up visit will be documented as having a missed visit and a protocol deviation (refer to **Section 12.5 - Deviations from Clinical Investigation Plan**) will be completed. The investigator will keep a record of documented follow-up attempts in the subject's file.

Table 2. Follow-up Schedule and Windows for Study Subjects

| Follow-Up Visit | Window Start Day | Target Day | Window Close Day | Follow up Method |
|---|------------------------------|----------------|------------------|---------------------------|
| Pre-Discharge | Within 72 hours of discharge | Discharge date | N/A | In hospital or Site visit |
| 30 Days (-3 /+14 days) | 27 | 30 | 44 | Site visit |
| 3 Months (± 30 days) | 60 | 90 | 120 | Site visit |
| 6 Months (± 30 days) | 152 | 182 | 212 | Site visit |
| 1 year (± 30 days) | 335 | 365 | 395 | Site visit |
| 2 years (± 30 days) | 701 | 731 | 761 | Site visit |
| 3 years (± 45 days) | 1051 | 1096 | 1506 | Site visit |
| 4 years (± 45 days) | 1416 | 1461 | 1506 | Site visit |
| 5 years (± 45 days) | 1781 | 1826 | 1871 | Site visit |
| Follow-up visit dates are calculated from the date of the index procedure | | | | |

9 ADVERSE EVENTS

9.1 Definitions / Types of Events

9.1.1 Adverse Event

An adverse event (AE) is any untoward medical occurrence, unintended disease or injury, or untoward clinical signs (including abnormal laboratory findings) in subjects, users or other persons, whether or not related to the investigational medical device.

This definition includes events related to the investigational medical device and the procedures involved. For users or other persons, this definition is restricted to events related to the investigational medical device.

An AE can therefore be any unfavorable and unintended sign (including an abnormal laboratory finding), symptom, or disease temporally associated with the use of a medicinal (investigational) product, whether or not related to the medicinal (investigational) product.

Note: Unchanged, chronic conditions are not adverse events and should not be recorded on the eCRF Adverse Event form. Pre-existing conditions that have not worsened are not considered AEs.

9.1.2 *Serious Adverse Event*

If the AE meets any of the criteria below, it is regarded as a serious adverse event (SAE).

- a) Death,
- b) Serious deterioration in health that either:
 - 1) Resulted in a life-threatening illness or injury, or
 - 2) Resulted in a permanent impairment of a body structure or a body function, or
 - 3) Required in-patient hospitalization or prolongation of existing hospitalization, or
 - 4) Resulted in medical or surgical intervention to prevent life threatening illness or Injury or permanent impairment to a body structure or a body function
- c) Fetal distress, fetal death or a congenital abnormality or birth defect

Note 1: This includes device deficiencies that might have led to a serious adverse event if a) suitable action had not been taken or b) intervention had not been made or c) if circumstances had been less fortunate. These are handled under the SAE reporting system.

Note 2: A planned hospitalization for pre-existing condition, or a procedure required by the CIP, without a serious deterioration in health, is not considered to be a SAE. Such events will not count toward the primary endpoint.

9.1.3 *Anticipated Adverse Events*

Table 3 summarizes the anticipated events that have been identified as possible complications from the Tendyne Mitral Valve System. Please also refer to the list of anticipated events in the Tendyne Mitral Valve System IFU.

Table 3. Anticipated Adverse Events

| | |
|--------------------------------|--|
| Adverse foreign body response | Foreign body response |
| Adverse reaction to anesthesia | Heart Failure, new or worsening |
| Allergic reaction | Hematoma |
| Anemia | Hemolysis |
| Annular dissection | Hypotension |
| Aortic insufficiency | Infection / Sepsis |
| Atrial or ventricular injury | Leaflet, chordal, papillary or ventricular rupture (resulting from mitral valvuloplasty, if performed) |

| | |
|--|---|
| Atrial Septal Defect (resulting from mitral valvuloplasty, if performed) | Liver failure |
| Bioprosthetic valve dysfunction | Mitral valve injury |
| Bleeding complications | Mitral valve prolapse / stenosis |
| Blood loss which may require transfusion | Myocardial infarction |
| Cardiac arrest | Obstruction |
| Cardiac arrhythmia, atrial or ventricular | Paravalvular leak |
| Cardiac perforation | Pain |
| Conduction defect with or without need for pacemaker | Pericardial effusion / tamponade |
| Damage to cardiac tissue and/or structures | Pleural effusion |
| Death | Pulmonary embolism |
| Decreased LV function and/or cardiac output | Pulmonary hypertension |
| Device embolism | Renal insufficiency or failure |
| Device erosion, migration or malposition | Respiratory difficulty, insufficiency, or failure |
| Device thrombosis | Stroke or transient ischemic attack |
| Embolism (air, blood clot, tissue, calcium, etc.) | Tear or damage to device |
| Endocarditis | Vascular and access-related complications |
| Esophageal irritation, stricture, or perforation | Worsening of mitral regurgitation |
| Fever | |

Normal post-operative sequelae or expected post-operative events do not need to be recorded as AEs unless they require physician prescribed pharmacologic and/or surgical intervention outside of the acute peri-operative period. A few common examples of normal post-operative sequelae or expected post-operative events include access-site pain, bruising, and events related to general anesthesia.

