9.4.2 SAE Reporting to Sponsor and IRB

SAEs may be reported by the subject, observed by the investigator, or documented in medical records and must be reported to the Sponsor on the Adverse Event eCRF. Additional information related to previously reported SAEs should be updated within the eCRF as soon as the information has been reviewed and verified by the investigator.

The investigator should report all SAEs to the Sponsor as soon as possible but no later than 3 calendar days from the day the study personnel became aware of the event or as per the investigational site's local requirements, if the requirement is more stringent than those outlined.

The investigator will further report the SAE to the local IRB according to the institution's IRB reporting requirements.

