9.4.5 Investigational Site AE Reporting Requirements to Sponsor

Investigators are responsible for preparation and submission to the Sponsor of all reportable AEs and DDs identified in the CIP. Adverse event reporting requirements are included in **Table 4**. All reports are subject to inspection and to the retention requirements described in **Section 13.4.1 Investigator Records**.

Table 4. Investigational Site AE Reporting Requirements to Sponsor

| Event | Investigational Site | Reporting timelines |
|-------------------|----------------------|--|
| AE | All Sites | AEs (not including normal or expected post-operative sequelae) must be reported as soon as possible after study personnel becoming aware of the event or as per the investigative site's local requirements, if the requirement is more stringent than those outlined. |
| SAE | All Sites | SAEs must be reported no later than 3 calendar days from the day the study personnel became aware of the event or as per the investigative site's local requirements, if the requirement is more stringent than those outlined. |
| UADE | All Sites | UADEs must be reported no later than 3 calendar days from the day the study personnel became aware of the event or as per the investigative site's local requirements, if the requirement is more stringent than those outlined. |
| Device Deficiency | All Sites | DDs must be reported no later than 3 calendar days from the day the study personnel became aware of the event or as per the investigative site's local requirements, if the requirement is more stringent than those outlined. |

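### Do the recording exemption and the near-miss note in Section 9.1 let serious events be miscounted in the 30-day primary endpoint?

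*Combined protocol and SAP*

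**What the plan says.** The primary endpoint (Section 3.1) combines Device Success with freedom from device- or procedure-related SAEs at 30 days, as classified by the CEC. Section 9.5 has the CEC adjudicate the SAEs that are reported.

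Section 9.1.2 defines an SAE as an AE that meets a listed criterion. Item b) requires a serious worsening of health, and its sub-items include b)3, "Required in-patient hospitalization or prolongation of existing hospitalization", and b)4, "Resulted in medical or surgical intervention to prevent life threatening illness or Injury or permanent impairment". Note 1 brings in device deficiencies that could have ended in an SAE under less fortunate circumstances, and closes by routing them through SAE reporting. Note 2 removes planned hospitalizations and protocol-required procedures from the primary endpoint. Note 1 has no matching sentence.

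Section 9.1.3 says that events which are normal or expected after the operation "do not need to be recorded as AEs unless they require physician prescribed pharmacologic and/or surgical intervention outside of the acute peri-operative period". It adds that "examples of normal post-operative sequelae or expected post-operative events include access-site pain, bruising, and events related to general anesthesia". Table 3 in the same section lists "Adverse reaction to anesthesia" as an anticipated event.

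On reporting, Section 9.4.2 states: "The investigator should report all SAEs to the Sponsor as soon as possible but no later than 3 calendar days". In Table 4 (Section 9.4.5) the AE row reads "AEs (not including normal or expected post-operative sequelae) must be reported as soon as possible", while the SAE row reads "SAEs must be reported no later than 3 calendar days from the day the study personnel became aware of the event" and carries no exemption.

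**The concern.** There are two apparent gaps, and they act in opposite directions.

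**(a) Recording exemption.** The test in Section 9.1.3 is whether treatment was needed and when, not whether the event was serious. The acute peri-operative period is not defined, in Appendix II or elsewhere. A site that took this sentence literally might leave out a drug-treated or stay-prolonging event that also meets an SAE criterion. The CEC would not see it, and the success proportion would be too high. Anesthesia events sharpen the doubt, because they appear both in Table 3 and among the examples that need no record.

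**(b) Near misses.** Note 1 places near-miss deficiencies under the SAE heading. Note 2, directly below, has an explicit endpoint exclusion and Note 1 has none. A harmless use error or labeling fault, corrected before implant, might then be counted as a device-related SAE. The success proportion would be too low.

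At stake is the count behind the study's primary endpoint, in a sample of at most 30.

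**Working it through.** The plan gives no expected rate, precision target or hypothesis (Section 10.1), so there is no stated figure to reproduce. The check is a comparison of sections, followed by a bound on size.

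**(a) Which events could be lost?**

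1. Sub-items b)3 and b)4 are not free-standing. They apply only where item b), a serious worsening of health, is met. A longer stay or a course of drugs is not by itself an SAE.
2. The exemption covers events that are normal or expected, and the examples begin with access-site pain and bruising. The overlap is therefore limited to events that are both expected and a serious worsening.
3. Section 9.4.2 covers all SAEs without exception. Section 16.4 repeats that all SAEs go to the sponsor.
4. Table 4 states the exemption in the AE row and leaves it out of the SAE row. That placement shows that it is meant for non-serious events.
5. Several serious events fail the endpoint through Device Success regardless of AE recording: procedural death or stroke (criterion 1) and unplanned device- or access-related procedures (criterion 3).
6. Table 3 lists possible complications, whereas the exemption concerns ordinary sequelae. An adverse reaction to anesthesia and an expected after-effect of it can be different things, so the two entries need not conflict.

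What remains is an event that is expected, is a serious worsening, is treated within the undefined period, and does not already fail Device Success.

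**(b) Can a harmless near miss reach the endpoint?**

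1. Note 1 concerns deficiencies that could have led to an SAE, so none occurred. Its closing sentence assigns a reporting route.
2. Under Section 9.1.2 an SAE must first be an AE, which Section 9.1.1 describes as an untoward medical occurrence, injury or sign. A labeling fault corrected before implant is none of these.
3. Appendix II defines both device-related and procedure-related in terms of an AE. The endpoint counts related SAEs, so a deficiency with no AE does not qualify.
4. Deficiencies have their own definition (Section 9.2), reporting section (9.4.4) and row in Table 4.
5. Note 2 deals with hospital stays and procedures that could otherwise be taken to meet b)3, so an explicit exclusion is useful there. Near misses without an AE need it less.
6. Technical failures of the device already fail Device Success under criteria 4a and 4b.

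**Size.** For x successes among n = 30, the exact 95% limits are the 0.025 quantile of Beta(x, n − x + 1) and the 0.975 quantile of Beta(x + 1, n − x). The starting count of 21 is an assumption.

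| Case | x/30 | Proportion | Exact 95% CI |
|---|---|---|---|
| Assumed true count | 21 | 70.0% | 50.6–85.3 |
| One serious event lost under (a) | 22 | 73.3% | 54.1–87.7 |
| One near miss counted under (b) | 20 | 66.7% | 47.2–82.7 |

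One subject is 1/30 = 3.3 points. The interval at 21/30 is 85.3 − 50.6 = 34.7 points wide. One case of each kind cancels.

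The chance of at least one affected subject is 1 − (1 − p)^30. For assumed p of 1%, 2% and 5% it is 26%, 45% and 79%. These values restate the assumed p. The documents give no frequency, so they are not evidence that such cases will occur.

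**The case for a change.** The strongest case on the other side concerns the order in which a site works. An SAE is defined as an AE and is reported on the Adverse Event eCRF (Section 9.4.2), so a coordinator who first asks whether an event is recordable as an AE could stop at Section 9.1.3. AE collection begins at registration (Section 9.4.1), which is the implant attempt (Section 4.2), so it starts in the very period to which the exemption applies. With up to 10 sites and no definition of the period, practice could differ. The CEC sees only what is reported, and no charter or analysis plan can restore an event that was never entered.

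Part of this stands. Section 9.1.3 has no express exception for seriousness, the period is undefined, and Note 1 lacks the endpoint sentence that Note 2 has. But a site that withheld a serious event would breach both Section 9.4.2 and Table 4. The exemption relates to recording as an AE and leaves the medical record untouched. The sponsor has access to source documents (Sections 11 and 12.9), and Section 13.2 requires source records that support the eCRF. Source review can therefore find a missed SAE, although the documents do not show how much source review the monitoring plan requires.

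For near misses, what is left is that Note 1 says SAEs include them. The CEC Charter and the separate SAP are not among the documents and may settle the point.

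**Conclusion.** The concern does not call for a change. Its observations about the wording are accurate, but other sections supply the reading that a sponsor, a site and the CEC would sensibly apply: serious events are reported whatever their expectedness, and a deficiency with no AE is reported without becoming a related SAE in the endpoint. What is left is a matter of missing detail. A clarifying clause would do no harm but would mainly restate Section 9.4.2 and the existing definitions.

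The possible effect is 3.3 points per reclassified subject at n = 30, in either direction, against an interval of about 35 points at the assumed 70% success rate. Net direction and size cannot be derived. Section 3 sets no pass/fail criterion and Section 10.1 tests no hypothesis, so no formal decision turns on such a shift.

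This rests on two assumptions: that sites follow Section 9.4.2 and Table 4 as written, and that neither the CEC Charter nor the SAP directs otherwise.
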